8.5.3. Enrolled Patients

A patient will be considered “enrolled” at the time of skin incision to introduce the EVOQUE System into the body. Enrolled patients will be assigned a unique identification number by the study Sponsor. The patient ID number together with the patient initials shall be used to identify the patient on all study-related documents.

A study procedure should be scheduled within 90 days of a patient signing an informed consent.

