8.6. Study Exit Criteria and Procedures

All patients that sign an informed consent document for this study will have the study exit reason documented in the medical record and on the appropriate eCRF. Patients may exit the study for any of the following reasons:

- **Screen Failure:** Patients who are consented to participate in the study, but do not fulfill enrollment criteria.

- **Study Device Attempted but Not Implanted:** Enrolled patient for whom the implant procedure was prematurely aborted will be followed either for 30 days (for only safety evaluations) OR until resolution, stabilization, or is adequate explanation of any implant-related AEs and then exited from the study. Examples include:
 - Procedure attempted (i.e. skin incision to introduce the EVOQUE System) but patient did not receive a study device
- **Study Device Re-intervention/Explant:** Patient who has a surgical re-intervention for study device explant will be followed for 30 days after the re-intervention for safety evaluations only or until resolution of any AEs related to the re-intervention and then exited from the study. Note: a patient who has a percutaneous re-intervention where the study device remains in place will continue to be followed for the duration of the study.
- **Withdrawal**
 - **Patient Withdrawal:** A patient may voluntarily withdraw from the clinical study at any time, without penalty or loss of benefits to which they are otherwise entitled.
 - **Physician Withdrawal:** An Investigator also has the right to withdraw a patient if s/he feels it is in the best interest of the patient to do so.
- **Patient death**
- **Lost to Follow-up**
 - If a patient cannot be reached for a follow-up visit, the Investigator will document contact efforts and/or efforts to obtain hospital records in the appropriate eCRF. If a patient cannot be reached in any way, or misses a visit, the patient will be considered “unable to contact” for that time interval.
 - After 3 documented unsuccessful attempts to make contact, a certified letter will be sent to the patient’s residence. If there is no response after a certified letter is sent, the patient will be classified as “lost to follow-up”.
- **Completion Per Protocol**

Withdrawn patients will not have any study follow-up visits or procedures after the time of study exit. All data collected up until the time of withdrawal, including imaging studies such as echocardiography scans, will be analyzed.

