Questionnaires (Patient completed)								
Kansas City Cardiomyopathy Questionnaire (KCCQ)	X				X	X	X	X
Patient Edema Questionnaire ^L	X				X	X	X	X
Patient Preference Survey ^M	X							
SF-36v2	X				X	X	X	X
Bloodwork^N								
βHCG (if applicable) ^O	X							
BNP or NT-proBNP	X		X	X	X	X	X	X
Coagulation Panel (PT or PTT; INR for patients on vitamin-K antagonist)	X		X	X	X	X	X	X
Complete Blood Count (CBC; including platelets)	X		X	X	X	X	X	X
Complete Metabolic Panel (CMP; including Albumin, Bilirubin, ALP, ALT, AST, creatinine, BUN)	X		X	X	X	X	X	X
GGT	X		X	X	X	X	X	X
Uric Acid and eGFR	X		X	X	X	X	X	X
Troponin or CK-MB	X		X	X				
Electronic Diary and Activity Monitoring Sub study - Up to 45 patients (upon FDA approval) at up to 10 sites								
eDiary Assessment (KCCQ, EQ-5D-5L, SF-12, mood questionnaire, and symptom burden) ^P	X (daily)					X (daily)		
Activity Monitoring ^Q	X (daily)					X (daily)		

A. Refer to Table 7 for assessment windows

B. Implant procedure should be scheduled within 90 days of consent. Patients who enter the procedure room but who do not have the study procedure attempted (at least skin incision to introduce the Edwards EVOQUE System) will be classified as “non-implanted” and will be followed 30 days for safety. These patients will be exempt from all other study follow up visit procedures.

C. Should be collected at the 30 day and 12-month follow-up visits according to the current version of the acquisition guide unless medically contraindicated or patient refuses.

D. See Appendix C for Katz Index of Independence in Activities of Daily Living

E. mRS will be conducted at baseline for all patients with a history of stroke. For patients who experience a stroke during the study, mRS will be conducted closest to 90 days post event. It is recognized that an assessment of stroke is incomplete without an appropriate measurement of the disability resulting from the stroke, hence, mRS closest to 90 days post event will be used to assess clinical disability. Every effort should be made to have a neurologist or neurology fellow perform the neurological assessments, or alternatively, a trained research team member certified in stroke assessment. mRS can be obtained by a certified research team member via phone interview with the patient or caregiver member if the patient is unable to visit the research office.

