10.4. Quality Control and Quality Assurance Procedures

Because of the potential for errors and inaccuracies in entering data into eCRFs, originals or photocopies of all relevant procedural records and reports, post-procedural examinations, laboratory and other test results may be kept on file in the Investigator's patient study files. Access to eCRFs and copies of test results must be available at all times for inspection by the study monitor.

All clinical sites will be audited periodically by a study monitor employed or contracted by the Sponsor for protocol adherence, accuracy of eCRFs, and compliance to applicable regulations. Evident patterns of non-compliance with respect to these standards will be cause for the site to be put on probation for a period of one month. If corrective actions are not subsequently undertaken, the clinical site will be asked to withdraw.

The Sponsor will provide data management through a secure, password protected EDC system accessible via the Internet. Passwords will be issued to appropriate data management personnel to ensure confidentiality and protection of the data by allowing variable levels of access to the computer system.

11. Adverse Event Reporting and Assessments

Adverse events will be captured for all study patients from the time of enrollment until the patient's participation has ended (i.e., completion of study, lost to follow-up, withdrawal of consent, or patient has died).

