12.2. Analysis Populations

Analysis will be performed for the Enrolled, As-Treated (AT), Per-Protocol (PP) populations defined below:

- **Enrolled Population:** all patients enrolled in the study, defined as patients who sign informed consent and have had the study procedure attempted (attempted defined as skin incision for study device). Enrolled population will be used for the safety analyses.
- **As-Treated Population:** is a subset of the enrolled population who have had the study device implanted at the exit of procedure room. The AT population will be the analysis population for performance and functional endpoint analysis.
- **Per-Protocol Population:** is a subset of the AT population who had no protocol deviations relating to inclusion and exclusion criteria for the trial.

Additional analyses of performance and safety data using the PP population will be performed if there is/are a clinically meaningful difference(s) from the enrolled and the as-treated populations.

The safety analysis will be performed for enrolled population with due consideration given to the respective required follow-up intervals and the performance analysis including device success, procedural success and clinical success will be performed for implanted population.

The echocardiographic and functional analyses will be a summarization of measures of hemodynamic performance including reduction of tricuspid regurgitation, NYHA Functional Class, 6-minute walk test, and Quality of Life based on the implanted population. Patients that undergo any type of repair or replacement procedure for the tricuspid valve will be excluded from the echocardiographic analysis at the time of the reintervention and summarized in a table.

Clinical endpoints including all-cause mortality, heart failure hospitalizations, and non-elective re-intervention related to the device will be analyzed based on implanted population.

For patients participating in the sub-study, a separate data analysis plan will be developed to analyze the actigraphy data collected from the activity monitor and electronic patient reported outcome data collected from the eDiary.

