#### 9.2 Adverse Events

All Clinical Events Committee (CEC)-adjudicated and site-reported AEs with onset on or after the procedure date (Day 0) after implant will be summarized by early events ( $\leq$  30 days) and late events (> 30 days) for the Enrolled Population. Summaries of incidence rates (counts and percentages) will be reported. SAEs will be summarized by early events ( $\leq$  30 days) and late events ( $\geq$  30 days) as well.

Edwards	Revision Date: August 1, 2022		Rev		For Use Only by Affiliates of Edwards Lifesciences	Page 17 of 18	
	Title	Statistical Analysis Plan for TRISCEND Study (2019-06)					

AEs with onset prior to procedure will not be collected. Listings for all AEs and SAEs that occur post-procedure in the Enrolled Population will be provided.

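### Patients who enter the procedure room but have no skin incision are promised 30 days of safety follow-up, yet the plan contradicts itself on recording their adverse events and reports them nowhere

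*Protocol*

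**What the plan says.** **Follow-up promised.** Protocol Section 8.21, Table 14 footnote B, addresses patients who enter the procedure room but in whom the procedure is not attempted, meaning no skin incision for the device. They "will be classified as “non-implanted” and will be followed 30 days for safety". The footnote adds: "These patients will be exempt from all other study follow up visit procedures".

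**Enrollment.** Protocol Section 8.5.3: "A patient will be considered “enrolled” at the time of skin incision to introduce the EVOQUE System into the body".

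**AE capture.** The opening of Protocol Section 11: "Adverse events will be captured for all study patients from the time of enrollment". SAP 9.2: "AEs with onset prior to procedure will not be collected". SAP 5.1 defines the index procedure as the moment of the first skin incision for the study device.

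**Exit category.** Protocol Section 8.6, under the heading for a device attempted but not implanted: "Enrolled patient for whom the implant procedure was prematurely aborted will be followed either for 30 days" or until implant-related events settle. The example given there is a patient with an incision who received no device.

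**Populations and outputs.** Protocol Section 12.2 and SAP 4 define the Enrolled population as patients who consented and "have had the study procedure attempted (attempted defined as skin incision for study device"). It is the widest population defined, and safety analyses use it. SAP 3.4.3 and 9.2 restrict the AE and SAE listings to it. The MAE endpoint is timed from enrollment (Protocol Section 5.1, SAP 3.1).

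**The concern.** A patient can be harmed in the procedure room before any incision. Protocol Section 3.3 names TEE and the use of anesthesia as sources of anticipated events. Table 4 lists anesthesia reactions, cardiac arrest and esophageal perforation, and Table 9 calls for TEE measurements before the procedure as well as after it. If such an event stops the case before incision, that same event keeps the patient out of the Enrolled population. Exclusion then depends on outcome, at least for these cases.

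Evaluating safety is the study's first stated objective, and its results are meant to guide later trial designs. Footnote B shows that follow-up of these patients was intended, but the plan gives the information no route into the results.

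**Working it through.** **1. The rules applied to a footnote B patient (consented, in the room, no incision)**

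| Question | Source | Answer |
|---|---|---|
| Followed for safety? | Table 14 footnote B | Yes, 30 days |
| Enrolled? | Protocol 8.5.3 | No; at most provisionally enrolled (8.5.2) |
| AEs captured? | Protocol 11; SAP 9.2 with 5.1 | Not provided for: capture runs from enrollment, and AEs before the procedure (dated by incision) are not collected |
| AEs captured? | Table 14 AE row at the index procedure; Protocol 11.2 | Suggested: AE assessment is marked at that visit, and investigators report all AEs |
| Exit category? | Protocol 8.6 | None fits: the aborted-procedure category is for enrolled patients, screen failure is for patients not meeting criteria, and withdrawal rules out further follow-up |
| In a safety population? | Protocol 12.2; SAP 4 | No |
| In an AE/SAE summary or listing? | SAP 3.4.3, 9.2 | No |
| MAE clock? | Protocol 5.1; SAP 3.1 | Undefined, because it starts at enrollment |

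The two AE-capture rows conflict. The population and listing rows do not: every planned safety output requires an incision.

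**2. How often this might arise**

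The documents give no rate of pre-incision stops, so the rates here are assumptions. With 200 patients brought to the room, P(at least one) = 1 - (1 - p)^200:
- p = 0.5%: 63% (1 expected)
- p = 1%: 87% (2 expected)
- p = 2%: 98% (4 expected)

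**3. Effect on the 30-day MAE rate**

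There is no plan figure to reproduce: SAP 2.3 says the sample size has no statistical justification, and no expected MAE rate is stated. The inputs are 200 enrolled (the planned maximum), k patients with no incision (assumed 2 to 6, that is 1% to 3%), m of them with an MAE (assumed 1 or 2), and x MAEs among the enrolled (assumed base rate 10% or 20%). Simple proportions are used, which SAP 8.1 plans alongside Kaplan-Meier.

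Difference = (x + m)/(200 + k) - x/200

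| k, m | Base 10% (x = 20) | Base 20% (x = 40) |
|---|---|---|
| 2, 1 | 21/202 = 10.4%, +0.4 | 41/202 = 20.3%, +0.3 |
| 2, 2 | 22/202 = 10.9%, +0.9 | 42/202 = 20.8%, +0.8 |
| 6, 1 | 21/206 = 10.2%, +0.2 | 41/206 = 19.9%, -0.1 |
| 6, 2 | 22/206 = 10.7%, +0.7 | 42/206 = 20.4%, +0.4 |

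The range is -0.1 to +0.9 points. The top of it needs every added patient to have an MAE. With no MAE among them the rate falls; for example, 40/206 = 19.4%, or -0.6. For scale, the 90% confidence half-width at 20% with 200 patients is 1.645 × √(0.2 × 0.8/200) = 4.7 points.

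**The case against.** **The events would be recorded anyway.** Footnote B orders follow-up for safety and hangs on the index-procedure column, where AE assessment is marked. Section 11.2 asks for all AEs, Section 8.5 enters every consented patient in the data capture system, and Section 8.6 requires an exit reason. This stands as far as it goes. A reader might infer from Section 11 that these patients have no AE capture at all, but the documents support only a contradiction. What the objection does not supply is an output. Entry in the database and an exit reason do not report AEs, and the SAP 5.1 fallback date for procedure forms showing no incision does not place the patient in a population.

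**Footnote B may be a misworded version of the Section 8.6 rule** for patients with an incision but no device. That is possible, and the reconciliation should settle it. If so, patients stopped before incision have no follow-up rule either.

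**The stakes are small.** The anesthesia and TEE events at issue are mostly not MAE components in themselves. A case may also stop for imaging, equipment or scheduling reasons, and this is a descriptive feasibility study with no decision threshold. All of that stands and limits the point to AE and SAE reporting. For patients who do reach incision, SAP 9.2 counts AEs by date from Day 0, so a same-day event before incision could still be summarized.

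**Oversight bodies.** A reader might also infer that the safety board and the annual report would miss these events. The documents do not support that. The board reviews aggregate trial data under a charter not provided (Section 14.1), and neither the annual AE summary nor the reporting of unanticipated device effects (Sections 11.7 and 15.7.3) is restricted to enrolled patients.

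**Conclusion.** The point holds as an internal contradiction with a reporting gap. Safety follow-up is promised to patients with no incision, the passages disagree on whether their AEs are recorded, and no planned safety summary or listing would show them. This rests on the text alone and needs no assumption about rates.

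The main loss is in AE and SAE reporting. It would be tempting to conclude that the 30-day MAE rate is materially understated. The documents do not support that: under the assumed inputs the shift is about -0.1 to +0.9 points, its sign is not fixed, and it is well inside the sampling error at 200 patients. The abort rate, the number of MAEs and the base rate are all assumptions. The correction is worth making because safety is the first objective and the stated rules leave harms before incision out of the reported results.

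**What to change.** 1. Reconcile Table 14 footnote B with Protocol Sections 8.5.3, 8.6 and 11 and SAP 4, 5.1 and 9.2. Say whether the footnote was meant for the Section 8.6 group, and give patients with no incision an exit category.
2. Keep enrollment and the Enrolled denominator at skin incision.
3. State in Section 11 that AEs are captured for every consented patient brought to the procedure room, from the start of anesthesia or procedural TEE, and align the SAP 9.2 sentence on AEs before the procedure.
4. Add to SAP 9.2 a separate count of patients with no incision and a 30-day AE/SAE listing for them, shown beside the Enrolled results.

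The cost is wording changes in both documents and one extra listing. Footnote B as written already plans the 30-day follow-up, and the MAE analysis is unchanged. The downside is a possibly slightly less favourable safety picture.

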9.1. Device Shipment

Devices will be transported to a study site after a Clinical Study Agreement is in place, applicable regulatory (e.g., IRB, FDA) approvals are obtained, and an eligible patient has been identified.

Devices will be provided to study sites on an as needed basis for scheduled implant procedures.

All investigational devices used in this study for investigational purposes will be labeled “Caution: Investigational Device, Limited by Federal (USA) law to investigational use.”

9.2. Inventory and Accountability Records

All device shipments will have inventory and shipment records. Devices may be hand carried to study sites by Study Sponsor personnel; will have delivery of investigational device documentation (e.g., packing lists, transfer of investigational product form, etc.).

The Investigator(s) or designee will take inventory of the product and complete delivery documentation with receipt date and signature. Both the study site and Sponsor will retain copies of these documents. The Investigator or designee will maintain a Device Accountability Log (as provided by the Sponsor) for all investigational devices that document their receipt, disposition, and return. The log will be kept with the documents for the clinical study and will be available for review during Sponsor monitoring visits. Only investigators trained and identified in the Delegation of Authority form on file at Edwards Lifesciences may use the investigational devices.

Use of the investigational devices and accessories provided for use in this study is prohibited outside of this study protocol.

9.3. Device Storage

The device inventory will be stored in a locked, controlled, cool and dry area as described in the IFU and/or presented on the device labeling. This secured area will only be accessible to the Investigators or approved designees.

9.4. Device Return

All device returns and dispositions must be captured on the Device Accountability Log.

The Investigator will receive instructions from the Sponsor on the return process, when applicable (e.g., Sponsor request, study is terminated, or product expiration, etc.).

All unused investigational devices (in original packaging, in opened packages, or removed from the original packaging) will be returned to the Sponsor, upon request.

Study devices suspected to have a device malfunction or deficiency should be returned to the Sponsor (see **Section 11.8 and 11.9** for more details).

9.5. Patient Implant Card

An implant card will be supplied to each patient implanted with the EVOQUE valve.

10. Data Collection and Reporting

The Sponsor will provide the study site with the clinical protocol, electronic case report forms, sample ICF(s), and all other necessary study-related documents. The Sponsor's Clinical Affairs Department, or designee, will conduct quality control and assurance of the study site, including but not limited to, data reviewing, data monitoring, and form collection. Every reasonable effort should be made to complete data entry in a timely manner.

10.1. Data Management

Sponsor will provide data management through a secure, password protected Electronic Data Capture (EDC) system accessible via the internet.

10.2. Electronic Case Report Forms (eCRFs)

Electronic case report forms (eCRFs) will be used to collect patient data during the study. The Investigator, or individual(s) designated by the Investigator, is responsible for entering all data from the study onto the eCRFs hosted on a dedicated website. Electronic CRFs must be fully completed for each patient and signed electronically by the investigator and/or designee. The eCRFs should be completed at the first earliest opportunity.

Data entered into the eCRFs may be subject to system validation checks (e.g., format range checks). System checks are automatic (i.e. generated at the time of data entry) and ensure the validity of submitted data. A query will be generated when a discrepancy requiring review has been identified. Discrepancies will remain open until a resolution is reached.

The site Investigator or designee must ensure the accuracy and completeness of the recorded data and then provide an electronic signature on the appropriate eCRFs. Changes to data previously submitted to the Sponsor will require a new electronic signature to acknowledge/approve the changes.

The Sponsor will conduct ongoing reviews of eCRF data. Sites that do not complete all data entry tasks in a timely manner may be prohibited from enrollment until data submission is current.

10.3. Source Documentation Requirements

All data that is entered in the eCRFs must have source documentation available in the patient medical records. Data to be collected for the study purposes must not be entered directly onto eCRFs. The data must be recorded from original source documents and available for review by the study monitor. Regulations require that Investigators maintain information in the study patient's medical records that corroborate data collected on the eCRFs. The source documentation may consist of but is not limited to: operative or procedure reports, progress notes, discharge summaries, laboratory reports, radiographic reports, medication logs, and worksheets. Source documents may be in electronic form and/or hard (paper) copies. Data recorded directly on CRFs such as patient-reported questionnaires or other data are deemed acceptable for collection outside of the EDC.

Protocol deviation information can be recorded directly on the protocol deviation eCRF.

